### **Ethics Approval:**

Approved by the Ethics Committee of the Faculty of Physical Education and Sport at Charles University (protocol no. 177/2020).

---

## **1. Background and Rationale**

Warm-up routines are essential in optimizing performance in competitive handball. Self-myofascial release (SMR) techniques such as foam rolling (FR) and the emerging method of tissue flossing (TF) have been shown to improve range of motion (ROM), reduce muscle stiffness, and potentially influence neuromuscular performance.

While FR is well documented, TF remains underexplored, particularly regarding its acute effects on explosive performance. Preliminary findings suggest TF may improve neuromuscular excitability through ischemic preconditioning and metabolic stress mechanisms. However, direct comparisons of TF and FR in major lower limb muscle groups relevant to explosive actions (e.g., countermovement jump [CMJ]) are lacking.

This study addresses this gap by comparing TF, FR, and control (CON) interventions on active range of motion (AROM), viscoelastic muscle properties, and jump performance in adolescent handball athletes.

---

## **2. Objectives**

### **Primary Objective:**

- To determine the acute effects of tissue flossing versus foam rolling on AROM, viscoelastic muscle properties, and jump performance.

### **Secondary Objectives:**

- To compare the magnitude and time course of TF- and FR-induced changes at 1 and 15 minutes post-intervention.
- To explore whether TF provides superior improvements in force development compared with FR and CON.

---

### 3. Study Design

- **Design:** Randomized, controlled, crossover study.
- **Conditions:**
  1. Tissue Flossing (TF)
  2. Foam Rolling (FR)
  3. Control (CON)
- **Population:** 30 male adolescent handball players.
- **Randomization:** Intervention order randomized using [www.randomizer.org](http://www.randomizer.org).
- **Washout:** Minimum 24 h, maximum 5 days between sessions.
- **Blinding:** Due to the nature of interventions, blinding participants was not feasible; however, outcome assessors were blinded to condition.

---

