#### Exclusion Criteria:

- Prior experience with TF.
- Regular use of FR.
- Contraindications to compression therapy or vigorous exercise.

**Recruitment:** Participants recruited from handball training centers in Prague.

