#### Sample Size Justification:

Power analysis (G\*Power 3.1.9.4) indicated  $n = 21$  required (effect size = 0.398,  $\alpha = 0.05$ , power = 0.8). To account for dropout, 30 participants enrolled.

---

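### The randomisation line does not require balance over the six TF, FR and CON sequences, although 30 participants allow exactly five per sequence

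*Protocol*

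**What the plan says.** Section 3 of the protocol calls the trial a "Randomized, controlled, crossover study" with three conditions (TF, FR, CON) in "30 male adolescent handball players". The allocation rule is "Intervention order randomized using" a named website, and nothing more. The set of sequences, the unit of randomisation, blocking and balance are not given. Sessions are separated by "Minimum 24 h, maximum 5 days between sessions".

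The primary objective in section 2 is "To determine the acute effects of tissue flossing versus foam rolling on AROM, viscoelastic muscle properties, and jump performance", so the contrast of most interest is TF against FR within the same athlete. Section 4 excludes players with "Prior experience with TF" and regular users of FR. Section 5 places assessments at baseline and at 1 and 15 minutes after the intervention. Section 6 names a two-way repeated measures ANOVA with Condition and Time as its factors. Session and sequence are not among them.

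The sample size paragraph gives a requirement of 21 and then states "To account for dropout, 30 participants enrolled".

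**The concern.** In a three-period crossover, session number is a nuisance factor. Athletes may change from session to session through novelty, familiarity with testing, or residual effects when sessions are only a day apart. If TF falls early more often than FR, any such change enters the TF−FR comparison.

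Equal use of the six sequences removes this by design while all participants complete, and with 30 participants it costs nothing. The randomisation line does not secure it. Allocation is settled before the first session, so an analysis plan written later can adjust for imbalance but cannot restore balance. For that reason the point belongs in the protocol.

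**Working it through.** **The protocol's own figure.** The only nearby figure is the required n of 21. It reproduces as a 3 × 3 within-subject interaction with f = 0.398, df = 4 and 4(21 − 1) = 80, and noncentrality 0.398² × 80 = 12.67, which gives power 0.8004. It does not bear on how sequences are allocated.

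**Inputs.** 30 participants and three conditions (section 3). Three conditions give 3! = 6 sequences, and 30/6 = 5 per sequence. Assumption, not in the protocol: each participant's sequence is drawn independently with probability 1/6 (simple randomisation).

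**Step 1: who is first.** Score each participant +1 if TF is first, −1 if FR is first, 0 if CON is first. The variance is 2/3, so the variance of (TF-first minus FR-first) is 30 × 2/3 = 20 and the SD is 4.47. Exact multinomial counts give:

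| Event, 30 participants | Probability |
|---|---|
| TF and FR equally often first | 0.089 (so unequal in 91%) |
| Difference of 4 or more | 0.44 |
| Difference of 6 or more | 0.22 |
| Exactly five in each sequence | 0.0004 |

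The mean absolute difference is 3.6 participants. All nine condition-by-session counts equal 10 in about 0.1% of randomisations.

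**Step 2: effect on TF−FR.** Suppose the outcome drifts linearly by s per session. The position of TF minus that of FR is ±1 in four sequences and ±2 in two. Its mean is 0 and its mean square is (4 × 1 + 2 × 4)/6 = 2. The chance shift in the TF−FR mean therefore has expectation 0 and SD √(2/30) × s = 0.26s. In simulation the 95th percentile of its absolute size is 0.50s. If the effect is confined to session 1, the SD is 4.47/30 = 0.15 times that effect, with 95th percentile 0.30.

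**Step 3: what s means.** Assessments include a baseline, taken here as one per session. For the Condition × Time interaction, a shift common to all time points of a session cancels, and s is then only a trend in the within-session change. For condition comparisons at 1 or 15 minutes without baseline subtraction, s is any trend in level.

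**Step 4: cost in precision.** The protocol gives no value for s, so a range is assumed. Let σ be the SD of an athlete's TF−FR difference without the trend. Under simple randomisation the variance becomes σ² + 2s², and the standard error grows by the factor √(1 + 2(s/σ)²):

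| s/σ (assumed) | Factor | Wider by |
|---|---|---|
| 0.1 | √1.02 = 1.010 | 1% |
| 0.3 | √1.18 = 1.086 | 9% |
| 0.5 | √1.50 = 1.225 | 22% |

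**Step 5: with five per sequence.** TF and FR each fall 10 times in sessions 1, 2 and 3, so the shift in step 2 is zero with 30 completers.

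**Step 6: carry-over.** In the six sequences TF directly follows FR in 2, follows CON in 2, and is first in 2. FR has the same pattern with TF in place of FR. With first-order carry-over c from the preceding condition, the TF−FR mean shifts by (c_FR + c_CON)/3 − (c_TF + c_CON)/3 = (c_FR − c_TF)/3. Balance does not remove this.

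**The case against.** The strongest objection is that the protocol does not state an unbalanced scheme. A reader might infer from the website that each athlete's order is drawn independently, but such a tool can equally produce a balanced list. The probabilities above are conditional on simple randomisation. This stands, and it limits the point to what the text fails to require.

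A reader might also infer that TF−FR will be biased. It will not be: the expected shift is zero. Under independent allocation the position effect is part of each athlete's own TF−FR difference, so the observed variance already contains it. The price is precision. The separate baseline also removes additive session shifts from the interaction. Both arguments stand.

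A third inference is that there is no practice session and that session 1 is therefore when the tests are learned. The protocol describes no practice session but does not rule one out. Its exclusions concern experience with the interventions, not with the outcome tests. The players have at least five years of handball, and the standard warm-up includes jumps. No session effect is quantified anywhere.

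Finally, it may be said that such detail can wait for the analysis plan. That holds for a period term. It does not hold for the sequence list, which must exist before the first session.

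**Conclusion.** The point holds as an inexpensive improvement to a loosely fixed design element. Section 3 permits an unbalanced allocation where exact balance is free, and the analysis named in section 6 does not adjust for session.

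If simple randomisation is used, unequal first-session counts are the rule (91%) and the TF−FR mean carries a chance shift of SD 0.26s. How much this matters depends on s, which is unknown, may be near zero, and for the interaction refers only to the within-session change. The document does not support calling the comparison biased or the allocation unbalanced in fact. Nor does the short minimum gap strengthen the case much, since balanced sequences still leave one third of any difference between FR and TF carry-over in the contrast.

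**What to change.** Replace the randomisation line in section 3 with: *Participants are randomised to one of the six sequences of TF, FR and CON from one permuted list with five per sequence (30 in total), concealed from the person enrolling until session 1.* The same website may be used to generate the list. If a balanced list has already been used, say so.

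Preferably include session in the model. Without it, position variation stays in the error term even when sequences are balanced, and the precision gained does not show in the standard errors. For the Condition × Time interaction the relevant term is session by time, because a session main effect alone cancels there.

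**Cost:** one sentence and one pre-generated list, with no added participants, sessions or staff. **Downside:** the last allocations can be predicted unless the list is concealed. Dropout will also leave some imbalance, since the sample size paragraph leaves room to fall from 30 to 21 completers. **Limit:** the change equalises session position and how often each condition follows each other one, but does not deal with unequal carry-over.

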### 4. Participants

#### Inclusion Criteria:

- Male handball players aged 16–18 years.
- $\geq 5$  years of playing experience.
- Injury-free in the last 3 months.

#### Exclusion Criteria:

- Prior experience with TF.
- Regular use of FR.
- Contraindications to compression therapy or vigorous exercise.

**Recruitment:** Participants recruited from handball training centers in Prague.

#### Sample Size Justification:

Power analysis (G\*Power 3.1.9.4) indicated  $n = 21$  required (effect size = 0.398,  $\alpha = 0.05$ , power = 0.8). To account for dropout, 30 participants enrolled.

---

### 5. Study Procedures

#### Warm-up (standardized for all sessions):

- 5 min cycling (100 W, 80 rpm)
- 10 squats, dynamic stretches (quadriceps, hamstrings, lunges, leg swings)
- 5 squats, 5 jumps @ 75% max

### **Interventions:**

- **TF:** Both thighs wrapped with elastic bands at 150% tension, followed by squats and lunges, then removal.
- **FR:** Quadriceps and hamstrings rolled for 30 sec per muscle per side.
- **CON:** Same exercises as TF, but without bands.

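### Does the lack of an exercise-matched control for foam rolling call for a change to the plan?

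*Protocol*

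**What the plan says.** Section 5 (Interventions) defines the three conditions in one line each. For the control, the line is "Same exercises as TF, but without bands". The flossing session is given as "Both thighs wrapped with elastic bands at 150% tension, followed by squats and lunges, then removal", so it combines the bands with exercise. The entry for foam rolling is "Quadriceps and hamstrings rolled for 30 sec per muscle per side" and mentions no exercise.

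The warm-up in the same section is common to every session. Nothing in the protocol adds the squats and lunges of TF and CON to the FR session.

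Section 1 presents the study as "comparing TF, FR, and control (CON) interventions". In Section 2 the primary objective is "To determine the acute effects of tissue flossing versus foam rolling on AROM, viscoelastic muscle properties, and jump performance". The first secondary objective is "To compare the magnitude and time course of TF- and FR-induced changes at 1 and 15 minutes post-intervention". The second asks whether TF improves force development more than FR and more than CON. Section 6 plans a Condition × Time repeated measures ANOVA with Bonferroni-corrected post hoc tests, and does not say which pairs will be tested.

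**The concern.** A control is normally expected to differ from each active condition only by the active ingredient. Here that holds for TF, where removing the bands leaves CON. It does not hold for FR: going from CON to FR adds rolling and also removes the exercises. If the squats and lunges improve an outcome, FR-CON understates rolling; if they tire the athlete, it overstates it. A larger sample or another model would not help, because the mismatch lies in the conditions themselves.

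The wording of the objectives adds to the worry. The first secondary objective attributes changes to FR, the third condition is called a control, and post hoc tests over all pairs would produce an FR-CON result. A reader could take that result as the effect of foam rolling. What is at stake is the claim that could be made about rolling on its own.

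**Working it through.** The point is structural, so the check is to write out what each contrast estimates and set it beside the objectives. The stated sample size (21 required, 30 enrolled) plays no part in it.

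**Inputs, all from Section 5.** Let *w* be the effect of the common warm-up, *e* the squats and lunges, *b* the band and *r* the rolling. Effects are taken as additive, which is a simplification.

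- TF = *w* + *e* + *b*
- CON = *w* + *e*
- FR = *w* + *r*

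**Contrasts.**

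- TF − CON = (*w* + *e* + *b*) − (*w* + *e*) = *b*
- TF − FR = (*w* + *e* + *b*) − (*w* + *r*) = *b* + *e* − *r*
- FR − CON = (*w* + *r*) − (*w* + *e*) = *r* − *e*

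So the observation is correct on the text: no contrast returns *r* alone, and FR − CON misses it by exactly *e*.

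**Objectives set beside the contrasts.**

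| Objective (Section 2) | Contrast needed | Status |
|---|---|---|
| Primary: TF versus FR | TF − FR | Valid for the two routines as delivered |
| Secondary 1: size and time course of TF and FR changes | Change from baseline in TF against change in FR | Valid, see below |
| Secondary 2: TF superior to FR and to CON | TF − FR and TF − CON | Valid; TF − CON is matched on exercise |

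No row needs FR − CON.

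**Secondary objective 1.** Outcomes are measured at baseline, 1 min and 15 min in every session. Let *t* be the time and retest effect at a given post-intervention time, common to all conditions. The change from baseline is *e* + *b* + *t* in TF and *r* + *t* in FR. Their difference is (*e* + *b* + *t*) − (*r* + *t*) = *e* + *b* − *r*, so *t* cancels without any use of CON. If baseline precedes the warm-up, *w* enters both changes and cancels too. The objective can therefore be met as a comparison of TF with FR.

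**Size of the mismatch.** It equals *e*, for which the protocol gives no value. The amounts in Section 5 do not settle it. Rolling takes 2 muscles × 2 sides × 30 s = 120 s, and no exercise amount is given for TF or CON. The warm-up before every session already contains 10 + 5 = 15 squats as well as lunges and 5 jumps, so a few more may add little. If *e* = 0, FR − CON equals *r*.

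**If the FR line is merely abbreviated** and FR sessions include the exercises, then FR = *w* + *e* + *r*, FR − CON = *r* and TF − FR = *b* − *r*. The concern then disappears, and the objectives can be met under this reading as well.

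**The case for a change.** The best case for a change runs as follows. The first secondary objective uses causal language about FR. The design gives TF a matched reference and FR none. A change from baseline in the FR session also contains time and retest effects, so on its own it does not show what rolling did. FR is a level of the ANOVA, so an FR-CON test is likely to appear, and nothing warns against reading it as the effect of foam rolling. A clarifying sentence would cost little.

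Much of this stands. FR-CON is rolling versus exercise and should be called that wherever it is reported. Likewise, a TF-FR difference cannot be credited to the band or the roller alone.

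The step from there to an amendment does not stand. The protocol draws no conclusion from FR-CON and nowhere says that CON isolates rolling. The first secondary objective sets the TF and FR changes against each other, and that comparison does not use CON. Matching the control to TF also fits the rationale in Section 1, which treats FR as the established method and TF as the less studied one: the new component is isolated, and FR serves as a comparator routine. The content of each condition is set out openly, so the meaning of FR-CON is visible to any reader. How a post hoc contrast is labelled is commonly left to the SAP, which was not available here, or to the report.

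The cost is small but real. Section 9 requires Ethics Committee approval for any amendment, and the past tense in Section 4 ("To account for dropout, 30 participants enrolled") suggests that recruitment is over.

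**Conclusion.** No change to the plan is needed. The observation is accurate: as written, CON is matched to TF only, and FR-CON estimates rolling minus exercise. But no stated objective uses that contrast, and the two that are used, TF-FR and TF-CON, remain valid as comparisons of the conditions as delivered. Choosing a control that isolates the band is a fair trade-off, and adding interpretive labels would alter no session, measurement, sample size, significance level or test.

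The size of the mismatch is the unknown effect of the squats and lunges. The protocol gives no basis for a figure, and zero is possible.

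This rests on two assumptions: that the one-line descriptions in Section 5 are complete, and that effects add. If FR sessions in fact include the exercises, the concern falls away altogether. If they do not, an analyst who reads Section 5 will describe any FR-CON result as rolling versus exercise.

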### **Outcome Measures:**

1. **Active Range of Motion (AROM):** Active Knee Extension (AKE) test.
2. **Viscoelastic Muscle Properties:** Stiffness and tone measured with MyotonPRO in VL, RF, and BF.
3. **Jump Performance:** CMJ height and braking rate of force development via force plate.

**Timing of Assessments:** Baseline, 1 min post, 15 min post intervention.

---

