### **6. Statistical Considerations**

- **Software:** SPSS v25.0; MATLAB for data organization/graphs.
- **Normality:** Shapiro-Wilk test.
- **Reliability:** Intraclass correlation coefficient (ICC) and coefficient of variability (CV).
- **Primary Analysis:** Two-way repeated measures ANOVA (Condition × Time).
- **Post Hoc:** Bonferroni correction.
- **Effect Sizes:** Cohen's d and partial eta squared ( $\eta^2$ ).
- **Significance Threshold:**  $p < 0.05$ .

---

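### The primary objective spans nine outcomes with none named primary, and the condition-by-time test is run at p < 0.05 with no stated control across outcomes

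*Protocol*

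**What the plan says.** Section 2 of the Protocol has one primary objective: "To determine the acute effects of tissue flossing versus foam rolling on AROM, viscoelastic muscle properties, and jump performance". It does not rank the three domains. One secondary objective touches the same ground: "To explore whether TF provides superior improvements in force development compared with FR and CON".

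Section 5, Outcome Measures, gives the variables behind each domain:

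- range of motion: the active knee extension test
- viscoelastic properties: "Stiffness and tone measured with MyotonPRO in VL, RF, and BF"
- jump performance: "CMJ height and braking rate of force development via force plate"

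Each is assessed at three times: "Baseline, 1 min post, 15 min post intervention".

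Section 6 names a two-way ANOVA, with condition and time both repeated, as the primary analysis. It sets one significance threshold, p < 0.05, and its only multiplicity provision is "Bonferroni correction", entered on the post hoc line. Section 4, Sample Size Justification, derives n = 21 from an effect size of 0.398, alpha 0.05 and power 0.8. It names neither the outcome nor the test, and adds: "To account for dropout, 30 participants enrolled".

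**The concern.** The Protocol does not say which outcome answers its primary question, nor what pattern of results across outcomes would count as an answer. The test called primary is repeated for every variable at an undivided 0.05. The Bonferroni entry belongs to the comparisons that follow the ANOVA, so as written it does not adjust the set of interaction tests.

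Two things are at stake. A single significant interaction among several could be presented as the answer to the primary objective, with more than a 5% chance of being false. And the power statement cannot be checked against the question it is meant to support, because it is attached to no outcome.

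**Working it through.** **The plan's own figure.** The documents do not name the test behind n = 21. Assume the 3 × 3 within-subject interaction, with numerator df (3−1)(3−1) = 4, denominator df 4(n−1), and noncentrality λ = f² × 4(n−1), where f = 0.398 and f² = 0.1584. At alpha 0.05:

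- n = 20: λ = 12.04, power 0.775
- n = 21: λ = 12.67, power 0.800

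This reproduces 21. The match is not unique: the formula for a between-within interaction with three groups, three measures and correlation 0.3 also gives 21.

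**Count of outcomes (Section 5).** Knee extension 1 + stiffness in three muscles 3 + tone in three muscles 3 + jump height 1 + braking rate of force development 1 = 9. Without the last, 8. The count takes one value per muscle and one knee extension value.

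**Error if the tests are independent.** The chance of at least one false positive is 1 − 0.95^k:

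- k = 9: 1 − 0.630 = 0.370
- k = 8: 1 − 0.663 = 0.337
- k = 3 (each domain reduced to one test): 1 − 0.857 = 0.143

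**Error if the outcomes correlate.** The documents give no correlations, so all of these are assumed. The interaction F test (4 and 116 df, n = 30) was simulated 20,000 times with all conditions equal and the same correlation between every pair of outcomes.

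| Assumed correlation | 9 outcomes | 8 outcomes |
|---|---|---|
| 0 | 0.374 | 0.339 |
| 0.3 | 0.332 | 0.306 |
| 0.5 | 0.278 | 0.257 |
| 0.7 | 0.217 | 0.204 |
| 0.9 | 0.134 | 0.129 |

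With n = 21 instead of 30 the results for nine outcomes hardly move (0.283 at correlation 0.5, 0.134 at 0.9).

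If only outcomes of the same domain correlate (the six MyotonPRO readings with each other, the two jump variables with each other), nine outcomes give 0.319 with both correlations at 0.5, and 0.213 with both at 0.9.

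**Effect of Holm.** Applied across the nine interaction tests with all conditions equal, it gives 0.052, 0.040 and 0.021 at correlation 0, 0.5 and 0.9. Applied across outcomes to the flossing-versus-rolling contrasts (the smaller p of the two post times, doubled, then Holm over nine), it gives 0.018 to 0.051, whether or not both interventions share an effect over control.

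**Power at the smallest Holm step,** 0.05/9 = 0.0056, under the same assumed 4-df test:

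| n | Power at 0.05 | Power at 0.0056 |
|---|---|---|
| 21 | 0.800 | 0.499 |
| 30 | 0.938 | 0.761 |
| 32 | 0.954 | 0.803 |

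**The case against.** **A SAP may settle this.** In part that stands. The SAP is not shown, and defining the post hoc family is ordinary SAP content, so its absence here is no fault. But the Protocol itself fixes the primary objective, the primary analysis and the threshold, and it sizes the study. Which outcome answers the primary question, and therefore carries the power statement, is a choice at protocol level.

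**The any-of-nine rule is not in the Protocol.** This is correct. Each domain could be reported as its own question, and whether separate questions need joint control is debated. The 13% to 37% therefore holds only if any significant interaction is taken as answering the primary objective. The Protocol neither adopts nor excludes that reading.

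**The wrong error is being measured.** A reader might infer that 37% is the chance of falsely declaring flossing better or worse than rolling. The documents do not support that. The figure concerns the omnibus interaction of three conditions by three times, and a flossing-versus-rolling claim would also have to pass the post hoc Bonferroni step. In simulation, with outcome correlation 0 to 0.5, that error is 7–27% if Bonferroni covers three pairs per time point and 1–3% if it covers all 36 pairs of cells. In each range the low end requires a significant interaction first, with all conditions equal, and the high end does not. At correlation 0.9 the ranges are 3–10% and about 1% or less.

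**Independence is unrealistic.** Six of the nine variables come from one device on the same thighs, so 37% is an upper case. The correction lowers the figure without removing the problem: at an assumed 0.9 between all outcomes it is still about 13%.

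**Force development is secondary.** Section 2 can be read that way, although Section 5 lists it under jump performance. Dropping it changes 37% to 34%.

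**Conclusion.** The concern holds in a limited form and should be fixed. Nine outcomes (eight on the narrower reading) sit under one primary objective with none named primary, and the only multiplicity provision does not reach the interaction tests. If any significant interaction counts as an answer and all conditions are equal, the chance of at least one false positive is about 13% to 37%: about 28% at an assumed common correlation of 0.5, and 21% to 32% if only same-domain outcomes correlate, at 0.9 down to 0.5.

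Two further readings go too far. These figures are not the chance of one isolated significant interaction. Exactly one occurs in 9 × 0.05 × 0.95^8 = 0.30 of trials under independence, and in about 18% and 5% at correlation 0.5 and 0.9, because false positives cluster. Nor are the power figures properties of this trial: they depend on the assumption that n = 21 came from the 4-df within-subject test, which Section 4 does not say.

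**What to change.** **If outcome data have not been seen,** the investigators name one primary outcome and one flossing-versus-rolling contrast, including its time point, and test it at two-sided 0.05. The other outcomes become secondary, and the Section 4 power statement is tied to that outcome and test. The cost is wording and a restated power basis. Section 4 reports enrolment in the past tense; if data have been seen, this choice would be post hoc and is no longer open.

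**Otherwise, one of two routes:**

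- Keep all outcomes and apply Holm across them to the condition-by-time tests, and also to the flossing-versus-rolling contrasts before any claim about that comparison. The cost is power. Under the assumed 4-df test, 30 completers have about 94% at 0.05 but about 76% at the smallest step, and 32 would be needed for 80%. If only 21 complete, power at that step is about 50%. The power should be restated.
- Label all results exploratory, report effects with confidence intervals, and make no confirmatory claim. This needs only wording, but gives up a confirmatory answer to the primary objective.
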